7.1.11 Nursing Implications

N/A

7.1.12 Reported Adverse Events and Potential Risks

N/A

8.0 CORRELATIVE/SPECIAL STUDIES

Prior to treatment during fiducial marker placement, needle biopsy of the prostate will be performed if the patient agrees (optional). Tissue from paraffin blocks will be used for biomarker quantification and correlative studies with treatment outcome.

At 2-2.5 years after completion of treatment (radiotherapy or androgen deprivation – whichever is longer) all patients, with or without documented failure will undergo transrectal needle biopsy of the prostate, unless clinically contraindicated or the patient refuses. For this biopsy procedure, 12-14 biopsies are recommended with cores taken from sextant regions plus the bilateral lateral base, bilateral lateral mid-prostate, and bilateral lateral apex. At least 2-3 of these biopsies should be from suspicious/Previously positive areas. The bilateral transition zone may be biopsied as well. Fewer biopsies may be obtained at the discretion of the urologist. The ultrasound is the true guidance imaging parameter that identifies the prostate boundaries and other nearby structures. The MRI is fused to the ultrasound such that the biopsies may be directed to a region in the ultrasound space. These data will enable us to evaluate the extent of disease eradication, as well as the prognostic significance of positive biopsies in men who are otherwise free of evidence of disease (low PSA and palpably normal prostate gland).

The 2 yr. post-treatment biopsy is for research purposes. If the biopsies contain prostate tumor cells, the results will be discussed with the patient and additional management considerations made apart from this clinical trial. Many times tumor cells are seen on prostate biopsies at 2-2.5 yr., but the cells show radiation treatment effect. In this situation, it is reasonable to continue to follow the PSA and re-biopsy a year later to look for clearance of the tumor cells. The strategy to re-biopsy will be up to the treating physician and will not be governed by the protocol.

9.0 MEASUREMENT OF EFFECT

Quantitative endpoints to assess study objectives are as follows:

9.1 Definitions

- *Biopsy failure rate*: The proportion of positive biopsy findings among patients without clinical or biochemical failure 2-2.5 years after completing study treatment (RT or ADT, whichever is longer).
- *Two-year failure rate*: The proportion of patients with either (i) biopsy failure 2-2.5 year after completing treatment (RT or ADT, whichever is longer) or (ii) evidence of biochemical and/or clinical failure (local, regional or distant failure) at any time prior to the planned 2 year post treatment biopsy.
- *Acute toxicity*: toxicity occurring during treatment and within three months of completing treatment
- *Late toxicity*: toxicity occurring more than three months after treatment completion.
- *Failure rate*: The cumulative incidence of biochemical or clinical failure allowing for competing risk as needed. Clinical failure is defined as at least local failure due to newly identified extension outside of the prostate after initial regression, or urinary obstructive symptoms with carcinoma found at TURP or regional/distant failure due to radiographic evidence metastasis (nodal or hematogenous spread). Biochemical failure is defined as $PSA \geq \text{nadir} + 2 \text{ ng/mL}$
- *Failure-free Survival (FFS)*: The elapsed time from start of radiotherapy to first documented evidence of biochemical or clinical failure or death from any cause, whichever occurs first. In the absence of any event defining failure, follow-up time will be censored at the date of last documented failure-free status.

- *Overall Survival (OS)*: The elapsed time from start of radiotherapy to death from any cause. For surviving patients, follow-up will be censored at the date of last contact.
- *Biomarker expression*: Quantification of the amount of the biomarker specific immunohistochemical staining in the area of tumor
- *QOL*: Two contemporary instruments will be utilized to assess patient function and bother (Expanded Prostate Cancer Index Composite-SF12 (EPIC-SF12) and the prostate cancer-specific anxiety Memorial Anxiety Scale for Prostate Cancer patients (MAX-PC).

9.2 Guidelines for Evaluation of Measurable Disease

9.2.1 Clinical primary tumor response will be measured by palpation and recorded in the following ways:

- Pretreatment: A representative drawing of the pretreatment tumor status on DRE, if palpable, will be recorded in the radiotherapy chart.
- Post-treatment: The change in palpable tumor extent will be recorded qualitatively using the definitions in Section 9.1.

9.2.2 PSA response: In 98% of patients treated with definitive radiotherapy there is a drop in PSA within 3 months. Those patients that have not responded should be investigated to define the site of progression (local-regional vs. distant metastases). In patients that have responded, a rising PSA later heralds relapse. Biochemical failure will be modeled after the Nadir+2 definition.(28) Evaluation of patients with a rising PSA profile will include a bone scan, MRI-pelvis/prostate, and prostate biopsy. ProstaScint scan has not been shown to be consistent for defining relapse pattern and is not recommended.

9.2.3 Nodal relapse will be scored as having occurred when appropriate clinical-radiographic evidence (CT or MRI evidence) of this becomes evident (biopsy proof not required in the presence of a rising PSA).

9.2.4 Hematogenous relapse will be scored as having occurred when appropriate clinical-radiographic evidence, shows this to be so (biopsy proof not required).

9.2.5 Quality of Life: As described in section 1.5, the EPIC-SF12 and MAX-PC questionnaires will be done at 6 weeks, 3 months, 9 months, 15 months and yearly to 5.25 years after radiotherapy.

10.0 MEASUREMENT OF TOXICITY

Acute proctitis and cystitis lasting for up to 3 months after completion of radiotherapy are accompaniments of radiotherapy for carcinoma of the prostate. The severity of these reactions is routinely evaluated during treatment and will be scored according to the criteria outlined in Appendix II. In our extensive experience, grade 3 or 4 acute toxicities are rare.

Delayed toxicities are usually related to urinary, rectal, and sexual function. The anticipated urinary and rectal toxicities and severity criteria are those shown in Appendix II. Other untoward clinical events will, however, also be documented.

11.0 ADVERSE EVENT REPORTING

The descriptions and grading scales found in the revised NCI Common Terminology Criteria for Adverse Events (CTCAE) version 4.0 will be utilized for adverse event reporting. A copy of the CTCAE version 4.0 can be downloaded from the CTEP web site (<http://ctep.cancer.gov/reporting/ctc.html>).

11.1 Definitions

11.1.1 **Adverse events** (AE's) will use the descriptions and grading scales found in the NCI Common Toxicity Criteria in Appendix II.

Adverse events: Any unfavorable and unintended sign (including abnormal laboratory finding), symptom, or disease temporally associated with the use of a medical treatment or procedure, regardless of whether it is considered related to the medical treatment or procedure (attribution of unrelated, unlikely, possible, probable, or definite). Each AE is a unique representation of a specific event used for medical documentation and scientific analysis.

Any laboratory abnormal value that leads to a change in subject management (eg, treatment discontinuation, requirement for additional medication or monitoring) or is considered to be of clinical significance by the investigator should be reported as an AE or SAE as appropriate, unless this value is consistent with the subject's present disease state or is consistent with values obtained prior to entry into the study.

11.1.2 A **serious adverse event** (SAE) is defined in the FDA CFR 312 as any adverse drug experience occurring at any dose that results in any of the following outcomes: death, a life-threatening adverse drug experience, inpatient hospitalization, or prolongation of existing hospitalization, a persistent or significant disability/incapacity, or a congenital anomaly/birth defect.

SAE's are defined by FDA and therefore seriousness (not severity) serves as a guide for defining regulatory reporting obligations for patient/subject safety. **Serious** is based on patient/event outcome or action criteria usually associated with events that pose a threat to a patient's life or functioning.

The definition of serious adverse event (experience) also includes **important medical events**. Medical and scientific judgment should be exercised in deciding whether reporting is appropriate in other situations, such as important medical events that may not be immediately life-threatening or result in death or hospitalization but may jeopardize the patient or **may require intervention** to prevent one of the other outcomes listed in the definition above. These should also usually be considered serious. Examples of such events are intensive treatment in an emergency room or at home for allergic bronchospasm; blood dyscrasias or convulsions that do not result in hospitalization; or development of drug dependency or drug abuse.

11.1.3 **Expected events** are those that have been previously identified as resulting from administration of the agent.

11.1.4 An adverse event is considered **unexpected** when either the type of event or the severity of the event is *not* listed in: the current NCI Agent-Specific Adverse Event List; the investigator's brochure, drug package insert or the drug information section of this protocol.

11.1.5 The definition of **related** is that there is a reasonable possibility that the drug caused the adverse experience.

11.1.6 An **investigational agent** is a protocol drug administered under an Investigational New Drug Application (IND). In some instances, the investigational agent may be available commercially, but is actually being tested for indications not included in the approved package label.

11.1.7 **Commercial agents** are those agents not provided under an IND but obtained instead from a commercial source.

11.1.8 **Concurrent administration:** When an investigational agent(s) is used in combination with a commercial agent(s), the combination is considered to be investigational, and reporting of adverse events would follow the guidelines for investigational agents.

11.1.9 **Sequential administration:** When a study includes an investigational agent(s) and a commercial agent(s) on the same study arm, but the commercial agent(s) is given for a period of time prior to starting the investigation agent(s), reporting of adverse events which occur prior to starting the investigational agent(s) would follow the guidelines for commercial agents. Once

therapy with the investigational agent(s) is initiated, all reporting of adverse events should follow the investigational guidelines.

11.2 Purpose

Adverse event data collection and reporting, which are required as part of every clinical trial, are done to ensure the safety of patients enrolled in the studies as well as those who will enroll in future studies using similar agents. Adverse events are reported in a routine manner at scheduled times during a trial (please follow directions for routine reporting provided in the Data Reporting Section). Additionally, certain adverse events must be reported in an expedited manner for timelier monitoring of patient safety and care. The following sections provide information about expedited reporting.

Events resulting from concurrent illnesses and reactions to concurrent medications must be reported as adverse events.

Any worsening of the patient's clinical condition while the patient is on study will be considered to be an adverse event unless it is within the normal range of disease fluctuation for that patient.

11.2.1 Determination of Reporting Requirements

Reporting requirements may include the following considerations:

- 1) whether the patient has received an investigational or commercial agent;
- 2) the characteristics of the adverse event including the grade (severity), the relationship to the study therapy (attribution), and the prior experience (expectedness) of the adverse event;
- 3) the Phase (1, 2, or 3) of the trial; and
- 4) Whether or not hospitalization or prolongation of hospitalization was associated with the event.

11.2.2 Steps to determine if an adverse event is to be reported in an expedited manner:

Step 1: Identify the type of event using the NCI Common Toxicity Criteria (CTC).

The CTC provides descriptive terminology and a grading scale for each adverse event listed. A copy of the CTC can be downloaded from the CTEP home page (<http://ctep.cancer.gov>). Additionally, if assistance is needed, the NCI has an Index to the CTC that provides help for classifying and locating terms. All appropriate treatment locations should have access to a copy of the CTC.

Step 2: Grade the event using the NCI CTC.

Step 3: Determine whether the adverse event is related to the protocol therapy (investigational or commercial).

Attribution categories are as follows: Unrelated, Unlikely, Possible, Probable, and Definite.

Step 4: Determine the prior experience of the adverse event.

11.3.1 All serious, unusual life-threatening or lethal adverse which may be study related will be reported within 24 hours by telephone to the Principal Investigator and must be followed by a written report which must be received by the Principal Investigator within 10 business days. The Principal Investigator shall also be responsible for promptly notifying the local Institutional Review Board of all such serious adverse events. For all fatal events (Grade 5) while on study or within 30 days of treatment, a written report will follow within 10 working days.

Hospitalizations scheduled only for study treatment will not be reported or collected as SAE's.

11.3.2 FDA Reporting

N/A

11.3.3 IRB Reporting

11.3.3.1 All adverse events that are serious adverse events **and** are unexpected **and** are related or possibly related must be reported to the IRB within ten (10) working days of being

made known to the Principal Investigator. Events that are more frequent than anticipated or more severe than expected must be reported to the IRB within ten (10) working days of being made known to the Principal Investigator.

All unanticipated deaths must be reported to the IRB within 24 hours of being made known to the Principal Investigator.

11.3.4 Follow-up Reporting

For all SAE's, the investigator is obligated to pursue and provide follow-up reporting information until the event has resolved or until an acceptable medical endpoint has been reached or the patient is lost to follow-up.

12.0 CRITERIA FOR DISCONTINUATION OF THERAPY

Treatment will be stopped for grade 4 acute toxicity (according to the current version of Common Terminology Criteria for Adverse Events (CTCAE version 4), but may be resumed per protocol if the treatment break is less than 10 working days. If grade 4 toxicity resolves beyond the 10 days the treating physician will decide whether to give additional RT.

Treatment will be stopped if metastasis is detected by radiographic or pathologic evidence and the patient will be removed from the study. A work-up for metastasis during treatment will only be carried out if the treating physician deems necessary.

13.0 DATA REPORTING

Data must be submitted according to the protocol requirements for ALL patients registered. Patients for whom documentation is inadequate to determine eligibility will generally be deemed ineligible.

A list of forms to be submitted, as well as expectation dates, may be found in Appendix IV.

14.0 STATISTICAL CONSIDERATIONS

14.1 Overview

This is a two-arm randomized Phase III trial with the primary objective of determining whether MRI-guided hypofractionated radiotherapy (HTIMRT), as compared with standard dose fractionation (SIMRT), reduces the two-year post treatment biopsy failure rate in men receiving primary radiotherapy for favorable to high risk prostate cancer. Secondary objectives include comparison of HTIMRT and SIMRT with respect to acute and late occurring toxicity, quality of life, biochemical and clinical failure, and survival. Additionally, blood and biopsy tissue samples from study patients will provide data for various biomarker studies described in the Bankhead Coley Team Science project "Integrated biomarkers for individualized prostate cancer therapy".

A single stage design without interim analysis of the primary endpoint is proposed for this trial. It would not be practical or desirable to suspend accrual for an extended period of time to accommodate an interim assessment of the two year failure rate as would be needed to consider early stopping for efficacy or futility (lack of efficacy) based on the main study endpoint.

14.2 Sample size, accrual rate and study duration

Study size is based on our primary objective of demonstrating that, compared to SIMRT, HTIMRT reduces the two year post treatment failure rate, by which we mean the proportion of patients with either biopsy failure or earlier evidence (within two years of treatment completion) of biochemical and/or clinical failure. (See definition in Section 9.1.) We expect the two-year failure rate in the standard fractionation arm to be 52.5%, representing the combined effect of a small rate of biochemical or clinical failure within two years, approximately 5%, and a relatively high rate of positive biopsy among the remaining 95% of patients, namely 50% ($0.05 + 0.95 \times 0.50 = 0.525$). This estimate is based on prior findings on randomized trials previously

organized by the PI. (75) Assuming equal allocation of patients to SIMRT and HTIMRT and sufficient follow-up to determine failure status at two years, a study size of 36 patients in each treatment arm provides 80% power to detect an absolute reduction of 30% in the two-year failure rate (biochemical, clinical, or biopsy), from 52.5% to 22.5%, using a one-sided Fisher's exact test with 5% significance level. To ensure a minimum of 72 study patients evaluable for the two year failure rate as our main study endpoint, we plan to enroll a total of 76 patients.

Based on an accrual rate averaging 2 patients per month, we plan to complete enrollment in 3.2 years. Patients will be followed for five years giving total study duration of 8.2 years. Analyses of some secondary endpoints, including acute toxicity, psychosocial parameters, biomarker distribution on ultrasound-guided biopsies, and initial MRI findings may be reported before the efficacy endpoints, including the primary endpoint. These secondary endpoints will be analyzed after all planned patients have been accrued, completed treatment and have a minimal potential follow-up of 3 months from the end of RT. The main efficacy endpoint requires less than five years follow up and will be performed after all patients have been assessed for two year post treatment failure status (2 yr. biopsy). Final efficacy analysis will be at the conclusion of study when patients have been followed for 5.25 years.

14.3 Definitions and endpoints:

Evaluable: Patients who are study eligible and receive an initial dose of radiotherapy, either SIMRT or HTIMRT will be considered *evaluable for safety*, regardless of whether or not the full course of radiation treatment is completed according to protocol. To be *evaluable for efficacy*, study eligible patients must complete radiation treatment and have follow up sufficient to include either the planned 2-year post treatment biopsy or earlier evidence of biochemical or clinical failure (within 2 years of treatment completion). These patients comprise the main analysis set.

Exclusions: Any patient who is enrolled on study but does not receive an initial dose of radiation treatment will be excluded from all efficacy analyses. Any patient who initiates treatment and is later found to be ineligible for study (e.g., protocol violation) will be withdrawn from study but will be followed for toxicity and clinical outcome; the experience of such patients will be characterized separately from that of patients who are evaluable for efficacy. Reasons for exclusion of enrolled patients from analysis of safety or efficacy will be characterized.

Study endpoints are defined in Section 9.1.

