14.5 Analysis plan

The main analysis of study findings will be done by treatment assignment (intention-to-treat) in all patients who meet evaluable criteria as stated in Section 14.3. We will report any instances of treatment crossover. As noted above, analyses of some secondary endpoints, including acute toxicity, psychosocial parameters, tissue and blood product-related biomarker distribution on ultrasound-guided biopsies, and initial MRI findings may be reported before the efficacy endpoints, including the primary endpoint. These secondary endpoints will be analyzed after all planned patients have been accrued, completed treatment and have a minimal potential follow-up of 3 months from the end of RT. An initial analysis of clinical outcome (efficacy) is

planned after all patients have been assessed for two year post treatment failure status and a final analysis will be done at the completion of the planned 5 year follow up of all study patients. Statistical tests comparing treatment arms will be one-sided with 5% significance level and stratified where appropriate by the factors considered in randomization.

Statistical analysis will include descriptive statistics for patient demographics and baseline disease characteristics, both overall and by treatment arm. Counts and percentages will be used to summarize the distribution of categorical variables while median, range, mean and standard deviation will be used for continuous variables. Baseline characteristics will include age, sex, race/ethnicity, T-category, Gleason score, PSA, risk group and performance status. Biomarker measurements and proteomic/genomic profiles obtained from baseline biopsy will also be summarized with descriptive statistics. (76)

Treatment received will be summarized by the type of RT and STAD components of therapy, the number and duration of treatment delays, and the rates of discontinuation or completion. Summaries will be provided for each treatment arm. Safety analysis will include a detailed tabulation of acute and late occurring toxicity by type and grade, both overall and by treatment arm. Additionally, we will estimate the cumulative incidence (from start of treatment) of grade 2+ and 3+ genitourinary (GU) toxicity and of grade 2+ and 3+ gastrointestinal (GI) toxicity in each treatment arm. Death without the toxicity of interest will be treated as a competing risk, and toxicity rates will be compared by treatment arm using Gray's test. (77, 78)

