14.6 Interim monitoring

The Research Team will continuously monitor study accruals, toxicities and clinical outcome. The Sylvester Comprehensive Cancer Center's Data and Safety Monitoring Committee (DSMC) will monitor this protocol according to the Cancer Center's DSM Plan. DSMC oversight of the conduct of this trial includes ongoing review of adverse event data and periodic review of trial outcomes. The DSMC also reviews reports from internal audits of protocol compliance and data integrity conducted by the University of Miami, Office of Research Compliance Assessment. Additionally, the Sylvester Protocol Review Committee will monitor study progress with respect to patient accrual.

Early stopping for excess toxicity. We propose the following guidelines for the Sylvester DSMC (see also Appendix III) in its review of accumulating data on toxicity of study treatment. The proposed guidelines were developed using Bayesian methods, which can be applied at any stage of enrollment without advance specification of the number of interim analyses to be performed, or the number of patients evaluable for toxicity at the time such assessments are made.(82, 83)

Under the Bayesian method, we assign a prior probability (level of belief at the start of the trial) to a range of possible values for the true toxicity rate. As data on treated patients become available, the prior probability distribution is revised and the resulting posterior probability becomes the basis for recommending either early termination or continuation of the study. Specific stopping guidelines based on posterior probabilities for both acute and late occurring toxicity are given below along with underlying assumptions for the prior distributions.

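### Safety set is conditioned on eligibility: treated patients later judged ineligible fall outside the by-arm toxicity comparison, and their place in the stopping guideline is unclear

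*Combined protocol and SAP*

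**What the plan says.** Section 14.3 opens the definition of *evaluable for safety* with "Patients who are study eligible and receive an initial dose of radiotherapy", in either arm, and adds that the full course need not be completed. The set is thus open to patients with incomplete treatment but closed to ineligible ones.

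The exclusions paragraph of the same section covers patients who start treatment and are afterwards found ineligible. They "will be withdrawn from study but will be followed for toxicity and clinical outcome; the experience of such patients will be characterized separately" from patients evaluable for efficacy. It then states: "Reasons for exclusion of enrolled patients from analysis of safety or efficacy will be characterized". Exclusion from the safety analysis is therefore foreseen.

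Section 14.5 runs the main analysis by assigned arm "in all patients who meet evaluable criteria as stated in Section 14.3". It names no other population for the toxicity tables, the cumulative incidence of GI and GU toxicity, or Gray's test.

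Section 13.0 widens the route to ineligibility: "Patients for whom documentation is inadequate to determine eligibility will generally be deemed ineligible".

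Section 14.6 says the Bayesian guideline needs no advance specification of the number of interim analyses "or the number of patients evaluable for toxicity at the time such assessments are made". That term is not defined. The worked examples there count patients randomized to one arm and assessed for toxicity, with no mention of eligibility.

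**The concern.** Toxicity follows from the radiation delivered, not from whether the patient met the entry criteria. A safety set should contain everyone exposed. Conditioning it on eligibility removes exposed patients from both numerator and denominator of the arm-level rates, on the basis of a judgement that can be made after treatment.

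Late reclassification is plausible. Section 14.3 provides for it, Section 13.0 allows it on documentation grounds, and the eligibility text is not uniform: the synopsis admits Gleason 6-10, while Section 3.1 admits 6-8. The trial is open-label as to treatment, and the plan does not require eligibility review to be finished, or blind to outcome, before toxicity is known.

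Two things are at stake: the by-arm toxicity comparison, which is a secondary objective, and the counts that the monitoring committee sets against Table 14.6.1. With about 36 patients per arm, one patient can matter.

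**Working it through.** **Inputs (Section 14.6).** Acute toxicity: prior Beta(0.3, 1.7), guideline met when P(rate > 15%) is at least 80%. Late toxicity: prior Beta(0.2, 1.8), guideline met when P(rate > 10%) is at least 80%.

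**Formula.** With x patients with an event among n assessed, P(rate > t) = 1 − F(t; a + x, b + n − x), where F is the Beta distribution function and (a, b) the prior parameters.

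**Reproducing the plan.**
- Acute 3/8: Beta(3.3, 6.7), t = 0.15, gives 90.4% (stated 90.4%).
- Late 2/8: Beta(2.2, 7.8), t = 0.10, gives 82.6% (stated 82.6%).
- Prior chances of exceeding the limits: 32.3% and 27.2% (stated 32% and 27%).

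The plan's figures are sound. The question is only who enters x and n.

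**Assumption.** The documents give no number of treated-but-ineligible patients. For illustration, exactly one patient is reclassified and removed from the counts.

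| Toxicity | Patient removed | All treated patients | After removal |
|---|---|---|---|
| Acute | with event | 5/20: 84.5%, met | 4/19: 71.1%, not met |
| Acute | with event | 3/8: 90.4%, met | 2/7: 74.9%, not met |
| Late | with event | 2/8: 82.6%, met | 1/7: 52.5%, not met |
| Late | with event | 3/16: 80.3%, met | 2/15: 57.9%, not met |
| Acute | without event | 4/17: 77.8%, not met | 4/16: 80.9%, met |

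**How typical the first four rows are.** For each denominator from 3 to 35, take the smallest event count (at least 2) whose posterior reaches 80%, then remove one patient with an event. The posterior falls below 80% at 27 of 33 denominators for acute toxicity and 28 of 33 for late toxicity. This describes sensitivity at the boundary; it is not the probability that such a case occurs.

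**Which set applies where.** For the toxicity tables and Gray's test, Sections 14.3 and 14.5 read together leave these patients out. For Table 14.6.1, the text supports two readings. If *evaluable for toxicity* means *evaluable for safety*, the eligibility condition applies. If the worked examples govern, every randomized patient assessed for toxicity counts. The two readings can give opposite recommendations on the same data.

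**The case against.** A reader might infer that the toxicity of these patients is lost. It is not. Section 14.3 requires that they be followed for toxicity, that their experience be described and that reasons for exclusion be reported. Section 13.0 requires data on all registered patients, and Section 15.5 requires a case report form for anyone who received any study treatment. The literal wording separates them from the efficacy-evaluable patients and does not spell out how their toxicity is to be shown. All of this stands. But a separate description is not inclusion in the arm-level rates or in the test comparing the arms.

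A reader might also infer that these patients are excluded from the stopping rule. The documents do not say so. Section 14.6 never cites the 14.3 safety set, and its examples carry no eligibility condition. The criteria are guidelines under which stopping is considered, and the monitoring committee reviews adverse events on an ongoing basis without restriction to an evaluable set. An event in a reclassified patient is not hidden from it. What remains is ambiguity in the formal count.

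A third tempting inference is that ineligibility would be declared because toxicity had occurred. Nothing in the documents supports that. The criteria are mostly baseline facts, a checklist and source documents are required at enrollment, and eligibility is confirmed again before randomization. These checks make late reclassification less likely, but Section 14.3 still provides for it.

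Finally, the numerical example is constructed, and the effect has no fixed direction. Both points are correct and are shown above.

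**Conclusion.** The concern holds in two parts of different strength. As written, Sections 14.3 and 14.5 leave irradiated patients later judged ineligible out of the by-arm toxicity rates and Gray's test. That is a stated rule, not a gap. For Table 14.6.1 the plan is ambiguous, not exclusionary.

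The size cannot be estimated, because it depends on an unstated number of reclassified patients; with none, there is no effect. With one, a guideline result near its boundary can change in either direction. No stated posterior, power or sample size figure is called into question. This should be corrected because the remedy is simple and the present definition has no advantage for a safety analysis.

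**What to change.** - **Section 14.3:** delete the eligibility condition and define the safety set as every patient who receives at least one fraction of protocol radiotherapy, regardless of any later eligibility review.
- **Section 14.5:** name this set for the toxicity tables, the cumulative incidence estimates and Gray's test.
- **Section 14.6:** replace the undefined term with this set, as the source of both numerator and denominator in Table 14.6.1, counting patients once they have been assessed for the toxicity in question.

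Patients found ineligible can still be listed separately as a supplement. The efficacy set, the sample size and the rule for assigning patients to arms in the analysis need not change; whether to analyse toxicity by treatment received is a separate matter. The cost is a short edit in three sections, with no new data collection, since these patients are already followed for toxicity.
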